6 SAMPLE SIZE JUSTIFICATION

In this study, 80 healthy smokers will be randomized in a 1:1:1:1 randomization ratio stratified by sex with an overall quota of 40% per sex to:

1. THS Blade device arm
2. THS Induction Mono device arm
3. THS Induction Mid device arm
4. CIG arm

Based on four previous similar studies conducted by PMP on the tobacco heating system ([ClinicalTrials.gov](#) identifiers are NCT01970995, NCT01989156, NCT01959932, and

Confidentiality Statement

Data and information contained in this document are considered to constitute trade secrets and confidential commercial information, and the legal protections provided to such trade secrets and confidential information are hereby claimed under the provisions of applicable law. No part of this document may be publicly disclosed without the written consent of Philip Morris Products S.A.

NCT01970982, respectively), [Table 7](#) contains estimates of geometric mean ratios (GMR) and associated coefficients of variations (GCV) for the (adjusted) contrast of a tobacco heating system against CIG. The effect of THS is expected to be similar on the selected BoExp. In addition, based on these studies, a conservative estimation of 15% of missing values may be expected for various reasons (e.g., withdrawals, mis-randomization, etc.).

Using the statistics displayed in [Table 7](#), the sample size planned for this study accounting for 15% of missing values (resulting in 20 subjects for each THS arms and 20 subjects in CIG arms, respectively), and a one-sided two-sample t-test (on the log-scale) with 2.5% type I error probability, the estimated power for each BoExp is displayed in [Table 7](#). By multiplying the power for each individual BoExp over the five to be tested in the primary hypothesis (per study), a global estimate of power for each THS arm is obtained. Assuming independence of the THS arms, the overall power of the study is equal or larger than $97\% = 99\%^3$ (to account for the 3 THS arms) for the primary objective.

Note that 10'000 simulations of one-sided two-sample t-test were also conducted to determine the 90 percentiles of the (upper) half-width of the 97.5%-confidence interval (CI) of the ratio between THS arms and CIG, as well as the 90 percentiles of the upper bounds of these CIs. These are also displayed in [Table 7](#). These provide indications on the expected precision on the estimates of the ratios. [Table 7](#) shows that the power of this study for the primary objective is expected to be at least 99%.

Table 7 Power Computation for Primary Objective

NCT (Region)	Endpoint	GMR (%)	GCV (%)	Individual Power	Study-wise Power	90%ile of the upper half width of the 95%-CI	90%ile of the upper bound of the 95%-CI
1970995 (JP)	3-HPMA	50.67	32.72	>99%	>99%	16.0	69.6
	2-CyEMA	18.23	32.43	>99%		6.2	27.8
	COHb	44.94	17.24	>99%		7.2	55.6
	MHBMA	13.49	58.68	>99%		10.1	28.6
	Total NNAL	43.69	26.09	>99%		11.9	60.6
1989156 (US)	3-HPMA	45.77	36.45	>99%	>99%	17.4	68.0
	2-CyEMA	17.21	45.68	>99%		9.9	35.0
	COHb	38.14	26.5	>99%		10.3	51.4
	MHBMA	12.58	76.92	>99%		15.9	35.4
	Total NNAL	43.81	40.7	>99%		18.7	69.7

Confidentiality Statement

Data and information contained in this document are considered to constitute trade secrets and confidential commercial information, and the legal protections provided to such trade secrets and confidential information are hereby claimed under the provisions of applicable law. No part of this document may be publicly disclosed without the written consent of Philip Morris Products S.A.

1959932 (EU)	3-HPMA	41.63	26.1	>99%	>99%	11.1	53.4
	2-CyEMA	13.16	34.41	>99%		4.0	18.6
	COHb	23.45	16.84	>99%		3.8	28.5
	MHBMA	8.38	54.57	>99%		5.6	18.2
	Total NNAL	43.54	27.13	>99%		11.8	61.8
1970982 (JP)	3-HPMA	52.86	39.57	>99%	>99%	21.4	79.5
	2-CyEMA	21.21	43.16	>99%		9.5	33.1
	COHb	47.1	16.08	>99%		6.9	56.1
	MHBMA	23.09	64.59	>99%		14.6	43.0
	Total NNAL	49.03	42.51	>99%		22.8	77.1

Of note, the GMR and GCV are assumptions extracted from the corresponding trial. The columns: individual power and study-wise power are computed through standard formulas. The columns: 90%ile of the upper half width of the 95%-CI and 90%ile of the upper bound of the 95%-CI are simulated values with 20 subjects per arms. The 90%ile of the upper half width of the 95%-CI is a simulated estimate of the precision for the corresponding BoExp. The 90%ile of the upper bound of the 95%-CI is a simulated estimate of the upper bound of the 95%-CI for the corresponding BoExp. Due to the independence of the distributions of the estimates, one cannot deduce the 90%ile of the upper bound of the 95%-CI with the GMR and the 90%ile of the upper half width of the 95%-CI.

A similar reasoning and assumptions for the key secondary objectives can be made. [Table 8](#) displays the power estimates for the key secondary hypothesis. As one can see, each THS arm thus each key secondary objective has a power of at least 99%. By multiplying the power for each objective ($\approx 99\%$) across all 6 objectives (1 primary (union of 3 objectives) + 3 key secondary), the power for all objectives altogether is then estimated to be at least 94% ($= 0.94 \approx 0.99^6$, assuming independence of the 6 objectives with a 99% power).

Table 8 Power Computation for Key Secondary Objectives

Study	Endpoint	GMR (%)	GCV (%)	Power	Overall Power	90%ile of the upper half width of the 95%-CI	90%ile of the upper bound of the 95%-CI
1970995 (JP)	2-NA	13.66	33.99	>99%	>99%	5.6	21.5
	3-HMPMA	43.06	35.59	>99%		18.5	72.2
	3-OH-B[a]P	27.19	43.93	>99%		12.9	46.4
	4-ABP	20.10	44.68	>99%		8.2	31.1

Confidentiality Statement

Data and information contained in this document are considered to constitute trade secrets and confidential commercial information, and the legal protections provided to such trade secrets and confidential information are hereby claimed under the provisions of applicable law. No part of this document may be publicly disclosed without the written consent of Philip Morris Products S.A.

	HEMA	50.14	34.79	>99%		14.8	63.2
	S-PMA	10.97	46.63	>99%		7.2	22.0
	Total NNN	27.02	61.84	>99%		23.6	59.9
1989156 (US)	2-NA	12.78	51.37	>99%	>99%	7.6	23.7
	3-HMPMA	38.26	53.56	>99%		21.7	67.8
	3-OH-B[a]P	28.94	54.77	>99%		24.2	67.7
	4-ABP	19.47	63.66	>99%		14.4	38.1
	HEMA	38.67	55.45	>99%		24.2	74.5
	S-PMA	12.58	69.68	>99%		9.6	23.5
	Total NNN	14.06	78.93	>99%		12.2	27.6
1959932 (EU)	2-NA	11.54	36.52	>99%	>99%	4.0	16.9
	3-HMPMA	22.54	30.76	>99%		6.5	31.4
	3-OH-B[a]P	27.50	46.17	>99%		14.0	44.1
	4-ABP	14.94	40.4	>99%		6.4	23.5
	HEMA	32.00	45.75	>99%		18.0	60.6
	S-PMA	5.99	37.3	>99%		2.0	8.3
	Total NNN	24.12	95.15	>99%		27.2	55.6
1970982 (JP)	2-NA	17.62	49.52	>99%	>99%	9.0	30.1
	3-HMPMA	37.71	49.07	>99%		21.3	63.3
	3-OH-B[a]P	29.99	52.2	>99%		19.4	51.9
	4-ABP	18.21	48.07	>99%		9.5	31.3
	HEMA	46.50	44.34	>99%		24.7	81.0
	S-PMA	15.68	49.76	>99%		8.2	25.5
	Total NNN	30.06	67.69	>99%		23.6	65.2

Of note, the GMR and GCV are assumptions extracted from the corresponding trial. The columns: individual power and study-wise power are computed through standard formulas. The columns: 90%ile of the upper half width of the 95%-CI and 90%ile of the upper bound of the 95%-CI are simulated values with 20 subjects per arms.

The 90%ile of the upper half width of the 95%-CI is a simulated estimate of the precision for the corresponding BoExp. The 90%ile of the upper bound of the 95%-CI is a simulated estimate of the upper bound of the 95%-CI for the corresponding BoExp. Due to the independence of the distributions of the estimates, one cannot deduce the 90%ile of the upper bound of the 95%-CI with the GMR and the 90%ile of the upper half width of the 95%-CI.

Confidentiality Statement

Data and information contained in this document are considered to constitute trade secrets and confidential commercial information, and the legal protections provided to such trade secrets and confidential information are hereby claimed under the provisions of applicable law. No part of this document may be publicly disclosed without the written consent of Philip Morris Products S.A.

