### **Sample Size and Evaluation:**

In this study, 80 healthy adult smokers will be randomized in a 1:1:1:1 randomization ratio to:

- THS Blade device arm
- THS Induction Mono device arm
- THS Induction Mid device arm
- CIG arm

This setting will provide more than 90% power to the trial to demonstrate a reduction for all BoExp tested in the primary objective for all THS study arms compared to the CIG arm, using a one-sided two-sample t-test with 2.5% type I error probability. This will also account for 15% data point loss due to missing, non-analyzable sample or major protocol deviation impacting evaluability of the primary objectives. This assumes, based on a similar study conducted by PMP S.A. (see [ClinicalTrials.gov](https://clinicaltrials.gov) Identifier: NCT01959932), that the geometric mean ratio (GM) and the related geometric coefficient of variation (GCV) of the ratio between all the THS study arms and the CIG arm are the following:

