#### 12.9.4 Determination of Sample Size and Power Consideration

In this study, 80 healthy smokers will be randomized in a 1:1:1:1 randomization ratio stratified by sex with an overall quota of 40% per sex to:

- THS Blade device arm
- THS Induction Mono device arm
- THS Induction Mid device arm
- CIG arm

Based on four previous similar studies conducted by PMP on the tobacco heating system ([ClinicalTrials.gov](#) identifiers are NCT01970995, NCT01989156, NCT01959932, and NCT01970982, respectively), [Table 13](#) contains estimates of geometric mean ratios (GMR) and associated coefficients of variations (GCV) for the (adjusted) contrast of a tobacco heating system against CIG. The effect of THS is expected to be similar on the selected BoExp. In addition, based on these studies, a conservative estimation of 15% of missing values may be expected for various reasons (e.g., withdrawals, mis-randomization, etc.).

Using the statistics displayed in [Table 13](#), the sample size planned for this study accounting for 15% of missing values (resulting in 20 subjects for each THS arm and 20 subjects in CIG arms, respectively), and a one-sided two-sample t-test (on the log-scale) with 2.5% type I error probability, the estimated power for each BoExp is displayed in [Table 13](#). By multiplying the power for each individual BoExp over the four to be tested in the primary hypothesis (per study), a global estimate of power for each THS arm is obtained. Assuming independence of the THS arms, the overall power of the study is equal or larger than 97% = 99% (to account for the 3 THS arms) for the primary objective

Note that 10'000 simulations of one-sided two-sample t-test were also conducted to determine the 90 percentiles of the (upper) half-width of the 97.5%-confidence interval (CI) of the ratio between THS arms and CIG, as well as the 90 percentiles of the upper bounds of these CIs. These are also displayed in [Table 13](#). These provide indications on the expected precision on the estimates of the ratios. [Table 13](#) shows that the power of this study for the primary objective is expected to be at least 99%.

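### The precision columns in SAP Tables 7 and 8 ignore the planned 15% loss and cannot be reproduced from the inputs shown; overall primary power has two different floors, 97% and 99%

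*SAP*

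**What the plan says.** SAP section 6 states that "80 healthy smokers will be randomized in a 1:1:1:1 randomization ratio stratified by sex", which is 20 per arm. It expects 15% missing values and describes the sample size as "accounting for 15% of missing values (resulting in 20 subjects for each THS arms and 20 subjects in CIG arms, respectively". Protocol 12.9.4 has nearly the same sentence, and the Protocol synopsis says of the power: "This will also account for 15% data point loss due to missing, non-analyzable sample".

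Power is computed with a "one-sided two-sample t-test (on the log-scale) with 2.5% type I error probability". Tables 7 and 8 then add two precision columns from 10,000 simulations, the 90th percentiles of the upper half-width and of the upper confidence limit. Section 6 presents them as indications of expected precision. The notes under both tables say the half-width and "90%ile of the upper bound of the 95%-CI are simulated values with 20 subjects per arms". Protocol Tables 13 and 14 carry the same columns and notes.

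For overall primary power, SAP section 6 first says "Assuming independence of the THS arms, the overall power of the study is equal or larger than" 97%, from 0.99 cubed over three THS arms. The next paragraph says Table 7 "shows that the power of this study for the primary objective is expected to be at least 99"%.

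**The concern.** There are three linked problems.

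1. Twenty is the randomized number per arm, so a simulation at 20 makes no allowance for the 15% loss that the same section plans for.
2. Some rows look wrong on inspection. In source study 1989156, total NNN has a larger GMR and a larger GCV than MHBMA, yet a smaller half-width and a smaller bound.
3. One quantity, overall primary power, is given two different floors.

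What is at stake is whether the figures offered as expected precision can be relied on and regenerated, and which power figure the sponsor stands behind. The sample size itself is not in question.

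**Working it through.** **Inputs.** From SAP section 6 and Tables 7 and 8: 80 randomized 1:1:1:1, 15% loss, one-sided 2.5%, and GMR, GCV, half-width and bound for 20 + 28 = 48 rows. Evaluable per arm: 80/4 × 0.85 = 17.

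**Assumption.** The documents attach the GCV to the adjusted contrast and do not define it further. I take log-SD σ = √ln(1 + GCV²), common to both arms.

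**Step 1: the plan's own power figures.** 0.99³ = 0.970 and 0.99⁶ = 0.941, as stated. With the noncentral t distribution, every individual primary power exceeds 99%: the minimum is 99.93% at n = 20 and 99.71% at n = 17. The power columns reproduce.

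**Step 2: precision columns.** Log-ratio estimate d ~ N(ln GMR, σ√(2/n)); pooled variance from chi-square with 2n − 2 df; upper limit = exp(d + t(0.975, 2n − 2) × SE); half-width = upper limit − exp(d). 90th percentiles over 400,000 draws.

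Example, MHBMA in 1989156: σ = √ln(1 + 0.7692²) = 0.682; true SE at n = 20 is 0.682 × √(2/20) = 0.216.

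| Row (half-width / bound, %) | Stated | n = 20 | n = 17 |
|---|---|---|---|
| MHBMA, 1989156 | 15.9 / 35.4 | 9.4 / 25.8 | 10.8 / 27.5 |
| HEMA, 1970995 | 14.8 / 63.2 | 14.8 / 71.5 | 16.6 / 73.8 |

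Rows differing by more than 5%:

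| | Half-widths | Bounds |
|---|---|---|
| n = 20 | 43 of 48 (all stated wider) | 24 of 48 (21 high, 3 low) |
| n = 17 | 38–39 of 48 (5 too narrow) | 24 of 48 (16 high, 8 low) |

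Monte Carlo standard error with 10,000 runs is about 0.04 to 0.15 points in the rows checked, far too small to explain these gaps. Other values of n, other confidence levels and other conversions of GCV to SD were tried; the best matched both columns within 3% in only 10 of 48 rows.

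**Step 3: ordering.** Under this model, bound/GMR should rise with GCV. In 1989156, MHBMA (GCV 76.92) gives 35.4/12.58 = 2.81 and total NNN (GCV 78.93) gives 27.6/14.06 = 1.96. Of 264 within-study pairs, 19 are inverted by more than 5% beyond rounding. No single increasing conversion of GCV to SD can produce that.

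**Step 4: check without the GCV.** Centre on the displayed GMR and leave the log-SD free. Find the SD that reproduces the row's stated half-width (±0.05), and read off the 90th-percentile bound at that SD. Repeat for arm-SD ratios of 1, 2, 4 and 1000, with pooled and Welch intervals: eight settings, n = 20. In 12 of 48 rows the stated bound is more than 5% away, beyond rounding, in all eight settings (4 too high, 8 too low). At n = 17, 10 of these rows remain.

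| Row | Half-width | Bound implied | Bound stated |
|---|---|---|---|
| HEMA, 1970995 | 14.8 | 70.6–71.7 | 63.2 |
| 2-CyEMA, 1989156 | 9.9 | 30.7–31.3 | 35.0 |
| MHBMA, 1959932 | 5.6 | 15.9–16.3 | 18.2 |

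**Step 5: overall primary power at n = 17.** Noncentrality = −ln(GMR) / (σ√(2/n)). For 1970982, 3-HPMA: σ = √ln(1 + 0.3957²) = 0.381; noncentrality = 0.6375/(0.381 × 0.343) = 4.87; power 0.9971. Total NNAL: 0.9986. The other three exceed 0.9999. The product over five biomarkers is 0.9957 per arm, and 0.9957³ = 98.7% over three arms (99.7% at n = 20). Simulating the shared CIG arm gives 98.8% with pairwise variance and 99.1% with variance pooled over four arms. The other three source studies give at least 99.9%.

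**The case against.** - **The 20 per arm is disclosed and loosely worded.** The section 6 sentence can be read as 17 inflated to 20 randomized, and the Protocol synopsis supports that reading. This stands for the power text. It does not help the precision columns, whose notes say plainly that they were simulated at 20.
- **GCV is not defined, and arm-specific variances may have been used.** True, so the 43 and 24 counts depend on an assumption. The check in step 4 does not use the GCV, and it still finds 12 rows in which the two columns disagree. That check does assume log-normal data, equal arm sizes, centring on the displayed GMR and the half-width definition used above.
- **The SAP says the bound cannot be deduced from the GMR and the half-width.** The check does not add them; it simulates both from one SD.
- **Two lower bounds do not contradict each other, and 99% may be a per-arm figure.** This is fair as logic, and the per-arm reading is plausible. But the sentence refers to the primary objective, which requires all three arms. At 17 per arm the result lies between 98.7% and 99.1% depending on the approximation, so 99% is not assured as a floor.
- **Nothing inferential changes.** This stands and sets the severity.

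**Conclusion.** The concern holds, as a minor point. By their own notes, the precision columns are given for more subjects per arm than the plan expects to analyse. They cannot be regenerated from the displayed inputs, and 12 rows are internally inconsistent whatever the GCV means, under the assumptions listed above.

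The columns are not generally optimistic: at 20 per arm every half-width discrepancy above 5% is on the wide side. Some bounds are nevertheless too favourable, the largest shortfall being HEMA in 1970995 (63.2 stated; 73.8 at 17 per arm). All recomputed bounds at 17 stay below 100%, the highest being about 82%.

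The 97% primary floor holds. So does the 94% figure for all objectives (98.4% at 17 per arm by the product method). The 99% floor fails narrowly by that method in one of four source studies. Sample size, test and success rule are unaffected.

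**What to change.** In SAP section 6:

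1. State that 20 are randomized and 17 are expected to be evaluable per arm after 15% loss.
2. Rerun both precision columns of Tables 7 and 8 at 17 per arm and document the inputs: how GCV enters, common or arm-specific variance, and the half-width definition. Alternatively, delete the columns.
3. Give one overall primary power floor, at least 97%, and remove the sentence claiming at least 99%.
4. For clarity only, say that the limit is that of a one-sided 97.5% interval, equivalently a two-sided 95% interval. The two labels are not in conflict.

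Carry the change into the protocol at its next revision. The protocol supplied is version 2.0; version 3.0, which the SAP cites, was not available for this review.

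The cost is one short simulation, or the deletion of two columns, and about three sentences. No stand-alone protocol amendment is needed, and sample size, test, success rule and analysis do not change.

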7 CHANGES FROM THE PROTOCOL SPECIFIED STATISTICAL ANALYSES

Clarification on exposure period and safety follow-up periods in sections [4.4.1](#), [9.6.4.4](#) and [9.6.5](#).

8 ANALYSIS SETS

8.1 Screened Population

The Screened Population consists of all subjects who signed the ICF and who underwent at least one of the screening procedures.

8.2 Full Analysis Set (FAS)

The Full Analysis Set (FAS) will consist of all the randomized subjects who have at least one post-randomization product use experience (either randomized to CIG or one of the THS arms) and who have at least one valid non-safety assessment after randomization. The FAS will be analysed by randomized study arm.

8.3 Per Protocol Set (PPS)

The Per Protocol Set (PPS) will be a subset of FAS and include all randomized subjects who fulfil key compliance criteria of the protocol, i.e., have no major protocol deviation impacting the evaluability of the primary objective (to be further described in the SAP). The PPS will be analysed by randomized study arm.

8.4 Safety Set (SAF)

The safety population will consist of all the subjects enrolled in the study with at least one exposure to THS (product test at Admission Day -2), and who have at least 1 valid value for a safety assessment. The SAF will be analyzed according to actual exposure arm.

8.5 Protocol Deviations

Protocol Deviations will be summarized by major with and without impact on evaluability of primary and key secondary objectives and minor categories for the PPS, FAS and SAF. All Protocol Deviation data will be listed.

Confidentiality Statement

Data and information contained in this document are considered to constitute trade secrets and confidential commercial information, and the legal protections provided to such trade secrets and confidential information are hereby claimed under the provisions of applicable law. No part of this document may be publicly disclosed without the written consent of Philip Morris Products S.A

8.5.1 Major Protocol Deviations

Protocol deviations are defined as any deviation from the procedures defined in the protocol. Major deviations will include, but are not limited to, the categories outlined in [Table 9](#).

Table 9 Major Protocol Deviations with Impact on Evaluability

Category	Description
Any violation of inclusion/exclusion criteria	Considered a major deviation. The blinded data review team will decide on whether it impacts evaluability.
Mis-randomization (wrong information provided to randomization system)	Considered a major deviation with impact on evaluability. Mis-randomized subjects will be classified according to their actual exposure arm for safety analysis.
Use of any nicotine or tobacco-containing product other than the assigned product during the exposure period	Considered a major deviation. The blinded data review team will decide on whether it impacts evaluability.
Assessments related to the primary and key secondary objectives performed outside the time tolerance (see Table 10)	Considered a major deviation. The blinded data review team will decide on whether it impacts evaluability.

8.5.2 Minor Protocol Deviations

Minor deviations may include, but are not limited to, use of concomitant medication and assessments performed outside the time tolerance (see [Table 10](#)).

8.5.3 Assessment Time Points and Assessment Time Windows

[Table 10](#) contains the list of assessments that have a time constraint and an acceptable tolerance.

Confidentiality Statement

Data and information contained in this document are considered to constitute trade secrets and confidential commercial information, and the legal protections provided to such trade secrets and confidential information are hereby claimed under the provisions of applicable law. No part of this document may be publicly disclosed without the written consent of Philip Morris Products S.A.

Table 10 Assessment Time Constraints and Time Windows

Related to Primary Objective	Assessment	Time constraint	Tolerance
No	Safety panel Blood sample at Day -1 and Day 6 or during early termination visit	After >= 6 hours of fasting	Not applicable
Yes	BoExp Blood sample at Day -1, 1,2,3,4 and 5	08:00 PM to 10:00 PM	+/- 15 minutes
Yes	24-hours urine	24h	+/- 1 hour

